**3) Inclusion and Exclusion Criteria\***

INCLUSION CRITERIA:

- a. >18y of age,
- b. Subject or proxy who can provide informed consent
- c. Positive SARS COV2 by PCR or as determined by clinical team

EXCLUSION CRITERIA:

- a. Adults or Proxy unable to consent
- b. Individuals who are not yet adults (infants, children, teenagers)
- c. Pregnant women
- d. Prisoners
- e. Patients expected to die within 24 hours or with a “do not resuscitate” order,
- f. Multi-organ failure,
- g. History of hypersensitivity or allergy to any component of the study drug,
- h. Ongoing massive surgical or unexplained bleeding,
- i. History of bleeding or clotting disorder,
- j. Severe traumatic brain injury (Glasgow Coma Scale <6),
- k. Spinal or multiple-trauma,
- l. Cancer (incurable/terminal phase) and/or patients receiving palliative care,
- m. Enrollment in another concurrent clinical interventional study
  - if considered interfering with this study objectives
- n. Per study team discretion, any condition(s) that may prevent safe treatment, preclude adequate evaluation or adding further risk to their underlying illness.

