**7) Study Endpoints\***

The Primary endpoint is change from baseline in the ISTH DIC Score to Day 9.

The Secondary endpoints include change from baseline D-dimers, Fibrinogen & Prothrombin time, length of hospital stay (days), mortality (%), and Pulmonary function (including Time (days) to mechanical ventilation and/or ECMO Duration (days) of new ventilator or extracorporeal membrane oxygenation (ECMO) use, Change from baseline SOFA and SOFA Respiratory sub-score, Number of venous thromboembolisms, Number of major bleeding events

Subjects discharged prior to completion of intervention would be classified as having a successful outcome. We anticipate that all cause morbidity will occur in 10-20% of the COVID study population, despite standard of care. We anticipate that these patients will be deficient in endogenous AT3.

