**8) Procedures Involved\***

Any member of the study team will discuss potential subjects with the clinical team for appropriate pursuit of informed consent and screening for eligibility.

75 eligible subjects, after consent, will have laboratory blood tests for further screening.

25 of those subjects with endogenous **AT3  $\geq$  100%** will continue with SOC.

50 of those subjects with endogenous **AT3 < 100%** will be will be randomly assigned to begin **SOC plus treatment with exogenous AT3 supplementation or only SOC** treatment. The randomization schedule will be established by a member of the study team that is not involved in the informed consent process.

They will all be followed up for laboratory blood tests, study endpoints and adverse events. If they do not meet entry criteria they will be excluded from the study.

[figure not shown]
Consented subjects will be scored according to The International Society of Thrombosis and Haemostasis Disseminated Intravascular Coagulation scale (ISTH DIC) on study visit days 1, 3, 5, 7, 9 and 11.

The SOFA score will be performed only when the parameter is obtained clinically and monitored for changes in patient status on study visit days 1, 3, 5, 7, 9 and 11. Each organ system is assigned a point value from 0 (normal) to 4 (high degree of dysfunction/failure). It will be calculated on admission and Day 11 using the worst parameters measured during the study visit day. If a parameter is not obtained clinically it will be voided for research purposes.

UM IRB# 20201048

AT3 in COVID-19  
January 24, 2022, Version 6.2

After enrollment and each 48h period (+/- 12 hours) thereafter, blood samples are collected and assayed for routine clinical coagulation and inflammation markers, including AT3 activity, D-Dimer, anti-Xa, fibrinogen, and prothrombin time until Day 11.

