## **9) Statistics\***

Statistical analyses will be performed using SPSS version 21 (IBM Corporation, Armonk, NY). Parametric data are reported as  $M \pm SD$  and nonparametric data are reported as median (interquartile range). Missing values for continuous variables are handled by applying imputation methods before calculating their statistics. The study population will be stratified into two halves based on the primary outcome of change from baseline SOFA and/or ICH DC. Those with the fastest rate of recovery are compared to those with the slowest rate of recovery. We expect that AT3 will correlate with rate of recovery and/or with one or more of the secondary outcomes. The demographics and physiologic variables in the fastest and slowest groups are compared using a t test or Mann-Whitney U-test, as appropriate. Categorical variables are compared using a  $\chi^2$  or Fisher's exact test, as appropriate. Statistical significance is determined at  $p < 0.05$ . Then multivariate models will be evaluated for predicting the primary or secondary outcomes, using various performance metrics, such as area under the receiver operating characteristic curve, sensitivity and specificity, positive predictive value, and negative predictive value, as we have described in multiple previous studies. In addition, propensity scores will be assigned for each patient based on a 1:1 fixed ratio nearest neighbor matching was performed to compare those with fastest or slowest recovery. A 1:1 fixed ratio nearest neighbor matching is performed to minimize bias without sacrificing power, as we have described in multiple previous studies.

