**Appendix A**

**ISTH DIC**, the score is increased by 2 points for abnormal baseline D-dimers (fibrin-related marker) and/or abnormal fibrinogen <1.0 gram/L level (1 point). This scoring algorithm was developed by the ISTH Scientific and Standardization Committee (SSC) committee on DIC and published in 2001. The ISTH DIC is a set of objective criteria for the diagnosis and severity of DIC with a score of  $\geq 5$  correlating with overt DIC, whereas < 5 does not rule out DIC but may indicate DIC that is not overt. The score is only appropriate for use in patients with an underlying disorder that is known to be associated with DIC; e.g., sepsis, severe immunological reactions, etc.

The ISTH DIC score is calculated using

- platelet count ( $\geq 100,000 = 0$ ;  $50,000-99,999 = 1$ ;  $< 50,000 = 2$ ),
- fibrinogen level ( $\geq 100 \text{ mg/dL} = 0$ ;  $< 100 \text{ mg/dL} = 1$ ),
- prothrombin time prolongation above upper limit of normal (ULN)
  - ( $< 3 \text{ seconds} = 0$ ,  $3-6 \text{ seconds} = 1$ ,  $> 6 \text{ seconds} = 2$ ),
- and D-dimer ( $< 2 \text{ times ULN} = 0$ ,  $2-4 \text{ times ULN} = 2$ ,  $> 4 \text{ times ULN} = 3$ ).

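### Fast and slow recovery are split on unadjusted change in scores with a floor of 0 and no entry minimum, so patients who were never abnormal are classed with patients who did not recover

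*Combined protocol and SAP*

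**What the plan says.** Section 7 fixes the primary endpoint: "The Primary endpoint is change from baseline in the ISTH DIC Score to Day 9". Section 9 then builds its group comparison on a split: "The study population will be stratified into two halves based on the primary outcome of change from baseline SOFA and/or ICH DC". I read the last abbreviation as the ISTH DIC score. The next sentence is "Those with the fastest rate of recovery are compared to those with the slowest rate of recovery". Rate of recovery is defined nowhere else. No rule is given for tied patients, unchanged patients or patients who enter at 0.

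Appendix A gives the components under "The ISTH DIC score is calculated using": platelets 0-2, fibrinogen 0-1, prothrombin time 0-2 and D-dimer 0, 2 or 3. SOFA in the same appendix scores six organ systems from 0 to 4 each.

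Section 3 asks for adulthood, consent and "Positive SARS COV2 by PCR or as determined by clinical team". It sets no minimum DIC score, D-dimer or SOFA, and at the severe end it excludes "Multi-organ failure". Section 8 scores ISTH DIC "on study visit days 1, 3, 5, 7, 9 and 11".

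Section 7 also counts discharge before the intervention is complete as a success. Section 9 does not say whether this enters the split.

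**The concern.** A raw change score measures recovery only in patients who have something to recover from. Here a normal patient who stays normal and an abnormal patient who makes no progress get the same value, 0, and both rank below any patient who improved, even one who is still abnormal.

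Section 9 expects AT3 to correlate with rate of recovery, and the fast/slow comparison is its first test of that. If the label partly records how abnormal patients were at entry, an AT3 difference between the halves may reflect baseline severity. One of the three groups (25 of 75) is chosen for AT3 at or above 100%. If those patients enter at 0 more often, which is an assumption, high AT3 would be pushed towards the slow half, against the relation the plan expects.

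**Working it through.** **1. What the scores allow.** The ISTH DIC maximum is 2 + 1 + 2 + 3 = 8, and every integer from 0 to 8 is attainable. SOFA runs from 0 to 6 x 4 = 24. From baseline b the best possible change is -b. At b = 0 the ISTH DIC change lies between 0 and +8; at b = 5 it lies between -5 and +3. It is the score that is bounded at 0; the change is negative in anyone who recovers.

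**2. Three patients under the stated rule.** A scores 0 at baseline and Day 9: change 0. B goes from 5 to 3: change -2, ranked above A. C stays at 5: change 0, tied with A.

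**3. Is a low entry score plausible?** In the 183-patient cohort cited in Section 2, 183 x 0.115 is about 21 deaths. DIC criteria were met by about 0.714 x 21 = 15 of these and 0.006 x 162 = 1 survivor, so 16/183 = 8.7%. In a cited series of 24, platelets and prothrombin time were normal or nearly so. Most patients would therefore enter below overt DIC, with little room to improve outside D-dimer. These figures do not give the share at exactly 0.

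**4. Size, by expected counts.** The plan states no figure to reproduce. Assumptions: N = 75; a share p0 enters at ISTH DIC 0; a share pi of the others improves; 15% of all patients worsen (11.25); ties break at random; 37 are fast and 38 slow.

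- Improvers: I = 75(1 - p0)pi
- At 0 on both days: Z = 75 x p0 x 0.85
- Tied at change 0: T = 75 - I - 11.25
- Slow places left for tied patients: 38 - 11.25 = 26.75, when I is at most 37
- Share of the slow half at 0 on both days: Z x (26.75/T)/38

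Example, p0 = 0.4 and pi = 0.5: I = 22.5, Z = 25.5, T = 41.25. The slow half holds 25.5 x 26.75/41.25 = 16.5 such patients, and 16.5/38 = 0.44. The other 35% of patients who stay at 0 fall in the fast half.

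| p0 | pi | Share of slow half at 0 on both days | Of those staying at 0, share in fast half |
|---|---|---|---|
| 0.2 | 0.3 | 0.20 | 41% |
| 0.2 | 0.5 | 0.27 | 21% |
| 0.2 | 0.7 | 0.34 | 0% |
| 0.4 | 0.3 | 0.36 | 47% |
| 0.4 | 0.5 | 0.44 | 35% |
| 0.4 | 0.7 | 0.56 | 17% |
| 0.6 | 0.3 | 0.49 | 51% |
| 0.6 | 0.5 | 0.55 | 45% |
| 0.6 | 0.7 | 0.63 | 37% |

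At 0.2/0.7, I = 42 exceeds 37, so every tied patient is slow: 12.75/38 = 0.34. A simulation of 3,000 trials per row agrees with the third column to within 0.01.

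**5. Baseline imbalance, by simulation.** With the other patients entering at 2-5, mean baseline in the fast v slow half was 2.5-2.8 v 1.9-2.2 (p0 = 0.2), 2.0-2.5 v 1.0-1.5 (0.4) and 1.4-1.8 v 0.6-1.0 (0.6). A separate run with p0 of 10-70%, pi of 30-70% and 0-20% worsening put the chance of being classed slow at 0.55-1.00 for baseline 0, against 0.22-0.49 for the others.

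**6. Sensitivity.** Suppose 20% of abnormal patients improve, 40% worsen, and 5% of those at 0 worsen. The fast half then has the lower mean baseline: 2.18 v 2.46, 1.56 v 1.91 and 1.00 v 1.32 at p0 = 0.2, 0.4 and 0.6. The mixing remains. At p0 = 0.4, I = 9, Z = 28.5, T = 46.5 and 19.5 worsen. The slow half takes 18.5 of the 46.5 tied patients, of whom 28.5 x 18.5/46.5 = 11.3 were at 0 throughout, or 30% of 38.

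**The case against.** The strongest reply is that Section 9 leaves a term undefined and does not state a faulty rule. Several parts of this stand.

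- **Ties.** A reader might infer that patients entering at 0 can never be classed fast. The table shows otherwise: when few improve, the cut falls among ties at 0, and up to about half of those staying at 0 land in the fast half. The missing tie rule matters.
- **Direction.** A reader might infer that the fast half has the higher baseline by construction. It does not, as step 6 shows. Section 2 reports hypercoagulability lasting at least 5-10 days, so little improvement by Day 9 is conceivable.
- **Early discharge.** If the Section 7 rule enters the split, and 50% of patients at 0 and 20% of the others are assumed to leave early, the chance that a patient at 0 is classed slow falls to 0.48-0.55. Baseline separation nearly disappears. Never-abnormal patients still form 14-50% of the slow half.
- **SOFA.** The split may use SOFA, on which inpatients may less often score 0, since a P/F ratio of 400 or below already scores a point. The sizes above are for ISTH DIC only.
- **Speed.** A reader might infer that the plan ranks size of change in place of speed. It names a rate and does not define it.
- **Reach.** A reader might infer that every model uses the fast/slow label. Section 9 aims the prediction models at the primary or secondary outcomes, which include mortality and length of stay. Baseline score is neither named nor excluded as a covariate in the models or the matching.

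None of this removes the core fault. On change from baseline, patients A and C are indistinguishable whatever the tie rule, and no passage assures adjustment for the baseline score.

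**Conclusion.** The point holds. Splitting everyone on unadjusted change in scores bounded at 0, without an entry minimum, gives a label that mixes never abnormal with failed to recover and is generally confounded with baseline severity. A fast/slow difference in AT3 cannot then be read as an association with recovery.

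The equal ranking of A and C is certain from Sections 3 and 9 and Appendix A. The size is not. The 20-63% share of the slow half rests on the assumed inputs in step 4, because the documents give no baseline distribution or improvement rate. The higher baseline in the fast half is the usual result under those inputs but can reverse. The effect shrinks if early discharge is ranked as success, which Section 9 does not say. The plan should be changed; the remedy is cheap.

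**What to change.** In Section 9:

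1. Analyse the association of AT3 with recovery with adjustment for the baseline score. Splitting on the residual from a straight-line fit to baseline is not a clean substitute: on this coarse score, baseline still separated the halves in simulation (AUC 0.28-0.58, where 0.50 is no separation).
2. Define recovery only among patients with a baseline score above 0. For ISTH DIC this means 1 or more, so that no baseline value is left unassigned. Apply the same rule to SOFA if it is used. In simulations where all abnormal patients entered at 2-5, this restriction brought the AUC of baseline score for the fast label to about 0.50, against 0.56-0.78 as planned. Adjustment is still needed, because a patient entering at 1 can improve by only one point.
3. Report patients who enter at 0 separately, as stayed at 0 or worsened.
4. If speed is meant, define it from the serial ISTH DIC scores on Days 3, 5, 7 and 9. The Appendix B flowsheet schedules SOFA only on Days 1 and 11.
5. State how ties, deaths and the Section 7 early-discharge rule enter the classification.

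The cost is wording and programming, since the ISTH DIC scores are already collected. The downside is that the recovery analysis uses fewer than 75 patients, by a number that cannot be known in advance.

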**4) Number of Subjects\***

The study population will be comprised of 75 patients assigned to one of three groups of 25 COVID (+) patients each.

The proportion of subjects with AT3 levels < 100% will be 50/50 randomization of which 25 subjects with AT3 <100% will be standard of care and 25 subjects with AT3<100% will be standard of care with exogenous AT3 supplementation. The third group will be subjects with AT3 levels  $\geq 100\%$ .

- a. 25 patients with endogenous AT3 >100% who receive standard of care only or
- b. 25 patients with endogenous AT3 <100% who receive standard of care only or
- c. 25 patients with endogenous AT3 <100% who receive standard of care plus supplemental AT3.

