### Dosing Rationale-

In those COVID(+) patients with an endogenous AT3 activity level <100% and at the discretion of the attending physician, Day 1 infusion of AT3 will be at a dose to be adjusted based on initial body weight up to 100 kg maximum and to a set target plasma activity level of 120% according to the following formula:

$$= \frac{(120\% - \text{baseline AT3}\%)}{1.4} \times \text{body weight (kg)}$$

Based on an example of an 85kg patient with a baseline AT activity level of 90%,

- The dose would be 1,821 units on a dosing schedule of Day 1, 3, 5, 7 & 9
- For a total of approximately 9100 units
- Each Thrombate III vial contains 500 units each reconstituted with 10 mL of Sterile Water for Injection, USP, the final concentration is approximately 50 units per mL.
- Requiring 4 vials per dose or 20 vials per patient

Each 85kg patient will receive ~9100 IU's over 5 doses requiring 20 vials

- (10% overage to account for any dose adjustments needed)
- therefore each patient would require 10,000 IU's
- for a total of 250,000 IU's or 500 vials for the study.

AT3 will be drawn every other day, pre-dose, for monitoring, and verification of 120% target plasma activity level. Dosing schedule will be as follows: Day 1, 3, 5, 7 & 9 a dose will be given if AT3 activity level remains less than 100% on those days, otherwise no dose will be given. Days refer to a 24 hour period.

Data to be collected from the medical record according to the Study Flowsheet (Appendix B) will include:

- a. Demographics: age, comorbidities, medical history, concomitant meds, vital signs, height and weight,
- b. ISTH DIC score and a Sofa Score,
- c. Laboratory values:
  - a. Platelets, PT, INR, PTT, D-Dimer, Fibrinogen, AT3 level, Anti-Xa,
- d. Outcomes:
  - a. Length of Stay, Mortality, change in PF ratio, Vent/ECMO days, # and severity VTE's, # and severity of bleeding events

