**13) Risks to Subjects\***

Hypersensitivity reactions, including anaphylaxis, are possible. Should symptoms occur, THROMBATE III infusion will be discontinued and appropriate treatment begun as per clinical judgement.

- Because THROMBATE III is made from human blood, it may carry a risk of transmitting infectious agents, e.g., viruses, the variant Creutzfeldt-Jakob disease (vCJD) agent and, theoretically, the Creutzfeldt-Jakob disease (CJD) agent.
- We will perform coagulation tests to avoid excessive or insufficient anticoagulation and monitor for bleeding or thrombosis. Assessment will be based on clinical findings at the discretion of the treating physician along with laboratory values of PT, PTT, Hemoglobin and Hematocrit analysis. Treatment may include heparin for excessive coagulation or blood transfusion for insufficient coagulation ultimately left to the discretion of the treating physician.

Two clinical trials were conducted in 33 subjects with congenital AT deficiency. Nine subjects (27%) experienced 29 adverse reactions which occurred during 17 of 389 infusions. There were no serious adverse reactions reported. The severity of adverse reactions was reported as mild or moderate, except for wound secretion and hematoma, which was severe.

Dizziness (12%), Chest discomfort (9%), Nausea (9%), Dysgeusia (6%), Pain (cramps) (6%), and each of the following were reported in 3% of the subjects: Chills, Wound secretion and hematoma, Vision blurred, Chest pain, Dyspnea, Intestinal dilatation, Pyrexia and Urticaria,

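### Section 9 names only a fast v slow recovery contrast, so the plan as written gives no randomised estimate of major bleeding added by AT3; the bleed count also starts at admission

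*Combined protocol and SAP*

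**What the plan says.** Section 4 sets up three groups of 25. Group a has AT3 at or above 100% and is not randomised. Patients below 100% are randomised 1:1 to group b, standard of care only, or group c, "25 patients with endogenous AT3 <100% who receive standard of care plus supplemental AT3".

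Section 7 and Appendix C list the number of major bleeding events as a secondary endpoint. Appendix C starts the count at admission and ends it at discharge. The data list under Dosing Rationale in Section 8 includes the number "and severity of bleeding events", and Appendix B records bleeding at discharge.

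Section 9 is the whole analysis plan. It halves the study population on the outcome and then states: "Those with the fastest rate of recovery are compared to those with the slowest rate of recovery". The propensity matching uses the same two halves. Two other sentences touch on secondary outcomes: "We expect that AT3 will correlate with rate of recovery and/or with one or more of the secondary outcomes", and "Then multivariate models will be evaluated for predicting the primary or secondary outcomes". Neither names a treatment term. Section 9 does not mention randomised arm, standard of care, bleeding or safety. Appendix C refers to a between-group summary for mortality only, and gives no method.

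**The concern.** The protocol identifies the hazard itself. Section 2 describes these patients as already at high risk of bleeding. The drug-interaction text in Section 13 says that AT3 strengthens the effect of heparin, whose dose may need lowering to avoid bleeding. Group b is the only randomised evidence of how much bleeding would have occurred without AT3.

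The recovery split cannot take its place. It is defined by what happens after treatment starts, and it mixes all three groups, with 25 of 75 patients (33%) outside the randomisation. A trial that infuses an anticoagulant could follow its plan to the letter and never set c against b for bleeding.

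The counting window is a second, smaller matter. Bleeds between admission and randomisation cannot be caused by allocation, yet the wording of Appendix C lets them into the endpoint.

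**Working it through.** The plan gives no bleeding rate, effect size or sample-size calculation, so there is no figure of its own to reproduce. All bleeding risks below are assumptions.

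**1. What the recovery contrast recovers.** Inputs: 75 patients, 25 treated (Section 4), so halves of 37.5. Assume that AT3 adds 10 points of bleeding risk and that the halves are otherwise equal. Then the slow-minus-fast difference = 10 × (treated share of slow half − treated share of fast half).
- Treated 33% in each half: 10 × 0 = 0.
- Treated 40% fast, 27% slow: 10 × (0.267 − 0.400) = −1.3 points.
- Treated 20% fast, 47% slow: 10 × (0.467 − 0.200) = +2.7 points.
- Extreme, all 25 in the slow half: 10 × 25/37.5 = +6.7 points.

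The 10-point effect is never recovered, and the sign depends on who recovers quickly.

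**2. What c v b would give at 25 per arm.**
- Exact upper 95% limit for 0/25: 1 − 0.025^(1/25) = 13.7%.
- Newcombe interval for 0 v 0: the Wilson upper limit of each arm is 3.84/(25 + 3.84) = 0.133, so 0 (−13 to +13 points).
- Newcombe interval for 3 v 1: Wilson limits are 0.042 to 0.300 and 0.007 to 0.195. Lower: 0.08 − √(0.078² + 0.155²) = −0.094. Upper: 0.08 + √(0.180² + 0.033²) = +0.263. So +8 (−9 to +26 points).
- Exact two-sided Fisher power with 4% in group b: 3.5% against 12% in group c, 23% against 20%, 78% against 36%.

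**3. Effect of counting from admission.** Let q be the risk of a major bleed before randomisation, equal in both arms, with later risks of 4% (b) and 12% (c). Patient-level risks become 1 − (1 − q)(0.96) and 1 − (1 − q)(0.88), so the difference is (1 − q) × 8 points. SE = √[p_b(1 − p_b)/25 + p_c(1 − p_c)/25].

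| q | Risk b | Risk c | Difference (points) | SE (points) | SE ratio |
|---|---|---|---|---|---|
| 0 | 4.00% | 12.00% | 8.0 | 7.59 | 1.00 |
| 1% | 4.96% | 12.88% | 7.9 | 7.98 | 1.05 |
| 2% | 5.92% | 13.76% | 7.8 | 8.35 | 1.10 |
| 4% | 7.84% | 15.52% | 7.7 | 9.02 | 1.19 |
| 8% | 11.68% | 19.04% | 7.4 | 10.15 | 1.34 |

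In a single trial, two earlier bleeders among the 50 randomised fall in the same arm with probability 2 × C(25,2)/C(50,2) = 24/49 = 49%. That moves the observed difference by up to 2/25 = 8 points. For a count of events rather than patients, the expected difference is unchanged and only noise is added.

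**The case against.** The best reply is that a by-arm bleeding comparison is left unstated rather than ruled out. The fast v slow tests are tied to demographic and physiologic variables. The next sentence, on tests for categorical variables, names no groups, and a bleed (yes or no) is categorical. The prediction models may cover secondary outcomes. A reader might infer that the plan forbids a c v b bleeding table, or that safety will be analysed by recovery half. The documents say neither. The gap remains, because no sentence supplies the comparison and the only grouping named is the wrong one for this question.

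A reader might also infer that bleeding goes unwatched. It does not. Section 12 pauses the study for any major bleed, with reporting to the FDA. Section 10 records SAEs from consent to discharge and requires an assessment of relatedness. Section 13 has the treating physician act on clinical findings and "laboratory values of PT, PTT, Hemoglobin and Hematocrit analysis". These protect patients but do not estimate excess risk against a control. The pause rule could also halt the trial before 25 per arm is reached, which would widen the intervals above.

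On the window, several replies carry weight. The protocol uses admission loosely: Section 8 has SOFA calculated on admission, while Appendix B puts it at enrolment, so study Day 1 may be meant. Exclusion (h), "Ongoing massive surgical or unexplained bleeding", does not reach a bleed that has stopped, but exclusions (i) and (n) could remove some earlier bleeders. AE entries carry start dates and times from consent onward. The values of q have no source, and 8% is twice the assumed later control risk.

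Finally, this is the safety part of a broader omission, since no endpoint has a named comparison of the randomised arms. That is true, and the remedy belongs inside the general one.

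**Conclusion.** The point stands. Section 9 followed as written yields no randomised estimate of major bleeding added by AT3. This is more than missing detail, because the one contrast it names answers a different question.

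The window is a lesser matter and depends on reading admission literally. Its cost is mostly noise: the standard error rises by 5% at q = 1% and by 34% at q = 8%. There is also a slight shrinkage of the patient-level difference, to 7.9 and 7.4 points respectively. Two stronger readings are tempting: that the window seriously biases the result, or that it has no systematic effect at all. The arithmetic supports neither. All of it rests on assumed risks of 4% v 12% and an equal q in both arms.

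Nor does it follow that a by-arm table could establish safety. At 25 per arm, no bleeds at all would leave differences of up to 13 points in either direction open. That limits what may be claimed, but it does not excuse leaving out the estimate.

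**What to change.** In Section 9, as part of a general comparison of group c with group b as randomised, add a descriptive bleeding analysis:
- Patients with at least one major bleed from randomisation to discharge, by arm, as n/N with exact 95% CI, and the difference (c − b) with 95% CI.
- Group a shown separately, outside the randomised comparison.
- Bleeds before randomisation listed separately, with Appendix C reworded to start the count at randomisation.
- A statement that the analysis is descriptive and supports no claim of safety.

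A written definition of a major bleed should go with it, since none appears in the text available and the term drives both this endpoint and the pause rule.

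By-arm tables of anti-Xa, aPTT, haemoglobin and anticoagulant use are optional. If included, use observed values rather than the Section 9 rule: "Missing values for continuous variables are handled by applying imputation methods before calculating their statistics". They would reflect heparin changes made after randomisation. Anticoagulant dose may not be recorded, because Appendix B lists concomitant medications only.

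The cost is one paragraph, one table, a definition and a date for each bleed. Bleeds logged as AEs or SAEs are already dated; those before consent would need the date taken from the medical record.

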**ClinicalTrials.gov Identifier**  
**NCT04899232**

**1) Objectives\***

This will be a prospective, randomized, open label, interventional pilot trial to test the hypothesis that deficient endogenous AT3 is associated with a prothrombotic hyperinflammatory state associated with COVID-19.

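### Section 9 relates AT3 to recovery in all 75 patients without fixing the AT3 time point or separating the infused arm, so the result cannot be attributed to endogenous AT3 if infusion affects outcome

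*Combined protocol and SAP*

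**What the plan says.** Section 1 (Objectives) sets out to "test the hypothesis that deficient endogenous AT3 is associated with a prothrombotic hyperinflammatory state associated with COVID-19".

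Section 4 (Number of Subjects) defines the population: "The study population will be comprised of 75 patients assigned to one of three groups of 25 COVID (+) patients each". Group a has AT3 at or above 100% and receives standard of care. The patients below 100% are randomised 1:1. Group b is "25 patients with endogenous AT3 <100% who receive standard of care only or" group c; group c is "25 patients with endogenous AT3 <100% who receive standard of care plus supplemental AT3".

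Under Dosing Rationale in Section 8, the infusion aims at 120% plasma activity. AT3 is drawn before dosing every other day, and on Days 1, 3, 5, 7 and 9 "a dose will be given if AT3 activity level remains less than 100% on those days". Appendix B schedules AT3 at every visit from Day 1 to Day 11.

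Section 9 divides the study population into two halves by recovery, compares the fastest with the slowest, and states: "We expect that AT3 will correlate with rate of recovery and/or with one or more of the secondary outcomes". That is its only statement about AT3. It gives no time point for AT3, and no exclusion, stratum or covariate for infusion. It specifies no comparison of groups a, b and c. The covariates of the multivariate models are not listed, and the propensity matching is described as comparing fast with slow recovery, not infused with uninfused patients.

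**The concern.** The AT3-recovery relation is the part of Section 9 that bears on the Section 1 hypothesis, and one third of the patients in it have been treated for the very deficiency under study. AT3 can be read in two ways.

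- **Day 1 AT3.** This value is endogenous in everyone, but 25 of the 50 low-AT3 patients are then assigned to infusion and no high-AT3 patient is. Infusion is therefore tied to low AT3, and any effect it has on recovery enters the correlation.
- **Later AT3.** Group c values can include infused AT3. They also reflect repeat dosing that depends on AT3 still being below 100%, so the level reached depends partly on the patient's own AT3 course.

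Either way, if infusion affects outcome, a positive, null or reversed correlation in the pooled 75 could not be attributed to endogenous AT3.

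**Working it through.** **Inputs from the documents.** Three groups of 25 give 3 x 25 = 75. The infused share is 25/75 = 33.3% of all patients and 25/50 = 50% of those below 100%. The infusion target is 120% and the cut between groups is 100%. Significance is at 0.05, taken as two-sided. The plan gives no effect size, SD or power, so there is no power figure of its own to reproduce.

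**Assumptions, not from the documents.** Baseline AT3 is truncated normal, with mean 110 and SD 8 in group a and mean 80 and SD 12 in groups b and c. Recovery has residual SD 1 (higher is better), and a true correlation with baseline AT3 of 0 or about 0.40. Infusion adds 0, 0.5 or 0.8 SD to recovery, or fully corrects it to the level expected at 120% AT3. Later AT3 is baseline plus noise of SD 8, and group c gains 15 or 35 points. The dependence of repeat dosing on AT3 is not modelled. Each scenario has 3,000 runs, and the statistic is the Pearson correlation, since Section 9 names none.

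**Day 1 AT3** (mean r, then percentage of runs with p < 0.05; ranges are over two sets of runs):

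| True r | Infusion effect | All 75, unadjusted | All 75, infusion term | Uninfused 50 |
|---|---|---|---|---|
| 0 | 0 | 0.00, 4-5% | 0.00, 4-5% | 0.00, 5% |
| 0 | 0.5 SD | -0.10, 12-13% | 0.00, 5% | 0.00, 5% |
| 0 | 0.8 SD | -0.15, 25% | 0.00, 5% | 0.00, 5-6% |
| 0.40 | 0 | 0.40, 95% | 0.37, 91% | 0.41, 86% |
| 0.40 | 0.5 SD | 0.31, 78-79% | 0.36-0.37, 91% | 0.40-0.41, 85-86% |
| 0.40 | 0.8 SD | 0.25, 57% | 0.36, 90% | 0.40, 85-86% |
| 0.40 | full correction | 0.17, 30-31% | 0.32, 80% | 0.41, 86% |

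With no true association, an effective infusion makes low-AT3 patients recover faster on average, so the false correlation is negative. The infusion term removes the distortion when the effect is constant. It does so only in part under full correction, because the effect then varies with baseline AT3.

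**Later AT3, all 75, unadjusted.**

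- *Group c raised by 35 points.* With no true association, infusion effects of 0.5 and 0.8 SD give false correlations of +0.10 and +0.16, with rejection in 13% and 26% of runs. With true r about 0.40 and an inert infusion, r falls to 0.22 and power to 48%.
- *Group c raised by 15 points.* There is no excess rejection without a true association (4-5%). With true r about 0.40, r is 0.27-0.33 and power 64-84%.

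**Cost of restricting to 50.** The standard error of Fisher's z is 1/sqrt(n - 3). The ratio is sqrt(72/47) = 1.24, an increase of about 24%. The smallest r detectable with 80% power is tanh((1.960 + 0.842)/sqrt(n - 3)), which is 0.32 for n = 75 and 0.39 for n = 50.

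**The case against.** The strongest reply is that the design already holds what is needed. AT3 is drawn before dosing, so the Day 1 value is endogenous in all 75, and that is the value the design uses to form the groups. Appendix B schedules AT3, the ISTH DIC score, D-dimer and fibrinogen at enrolment, so a Day 1 association could be examined before any infusion. Groups a and b supply 50 patients with no study infusion. Appendix C lists mortality between groups, and the multivariate models might include arm. The AT3 sentence is an expectation, not a fully specified test.

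Much of this stands, and it rules out three stronger readings that a reader might infer.

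- *That the plan mixes endogenous with infused AT3.* This happens only if values after Day 1 are used, and Section 9 does not say they are.
- *That the trial cannot test its hypothesis.* The planned data can examine it. The weakness is in the analysis as written.
- *That pooling must give a wrong answer.* With an inert infusion, pooling on Day 1 AT3 leaves r at 0.40 with 95% power, and a 15-point rise in later AT3 produces no excess rejection when there is no true association.

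The reply does not remove the omission. Nothing in the documents separates the infused arm in the AT3-recovery analysis. A covariate that might be included is not a planned adjustment, and the between-groups wording in Appendix C is attached to mortality only.

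**Conclusion.** The point holds in a conditional form. Section 9 leaves the AT3 time point open and pools the infused arm without adjustment, so the pooled correlation cannot be attributed to endogenous AT3 if infusion affects outcome. The plan cannot assume that it does not, because infusion is the treatment under study.

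The bias can run in either direction. On Day 1 AT3, a true r of about 0.40 fell to between 0.31 and 0.17 across the effective-infusion scenarios, and false rejection reached 12-25% when there was no association. These sizes rest on assumed AT3 distributions and infusion effects, and show direction and range only. They are not estimates for this trial.

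**What to change.** State in Section 9 that the association of endogenous AT3 with recovery and the secondary outcomes uses the pre-dose Day 1 AT3 value, in one of two ways chosen in advance:

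1. all 75 patients, with a term for assigned infusion; or
2. groups a and b only (n = 50).

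State also that AT3 measured after Day 1 in group c is not used as a measure of endogenous AT3.

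The change is to wording only, with no new samples or visits. Option 1 keeps all 75 but assumes a roughly constant infusion effect. Option 2 avoids that assumption, at the cost of the 24% larger standard error shown above. Under either option the association remains observational. Patients are not randomised to their AT3 level, so illness severity may confound it, and the report should say so.

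The randomised comparison of group c with group b answers a different question and should be analysed separately.
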